- 3) To evaluate the effects of active mental relaxation on anal resting and squeeze pressures. Our hypotheses is that mental relaxation will reduce anal resting pressure via  $\alpha_1$  adrenoreceptors; hence the  $\alpha_1$  adrenoreceptor antagonist will attenuate the reduction in anal resting pressure resulting from mental relaxation in healthy people and defecatory disorders.
- 4) To compare rectal compliance and the response to sinusoidal oscillation. Our hypotheses are that rectal compliance is higher and the contractile response to sinusoidal oscillation is lower in defecatory disorders than in healthy people.
- 5) To explore the effects alfuzosin on bowel symptoms in patients with chronic constipation. Our hypotheses are that alfuzosin will improve bowel symptoms in chronic constipation.

**6) To evaluate the role of microbiota in the relationship between stress/relaxation and defecatory mechanisms. Our hypothesis is that the susceptibility to stress is associated with differences in fecal microbiota. B. Research Design and Methods**

This study comprises 2 parts. Part A will compare the effects of oral alfuzosin (IR 2.5 mg) and placebo on anorectal functions on 1 day in all subjects (controls and patients). Part B will compare the effects of oral alfuzosin ( 10 mg ER) and placebo on bowel habits in constipated patients (but not in healthy subjects). 36 healthy women and 36 women with defecatory disorders will be enrolled in this study. This protocol is limited to women only because the vast majority of patients with constipation and defecatory disorders in our practice are women.

1. Human subjects.

- a) Inclusion Criteria for Controls (Part A only)
  - i. Healthy women volunteers aged 18-80 years
  - ii. Able to provide written informed consent before participating in the study

- iii. Able to communicate adequately with the investigator and to comply with the requirements for the entire study.

b) Inclusion Criteria for Patients (women aged 18-80 years) (Parts A and B)

- i. Constipation. Women with chronic constipation for 1 year with any 2 or more of the following symptoms for 3 months or longer, i.e. <3 bowel motions/week, straining  $\geq 25\%$  of time, hard or lumpy stools  $\geq 25\%$  of time, incomplete evacuation  $\geq \square 25\%$  of time, feeling of anorectal blockage  $\geq 25\%$  of time.
- ii. Able to provide written informed consent before participating in the study

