- iii. Able to communicate adequately with the investigator and to comply with the requirements for the entire study.

c) Exclusion Criteria for Controls; Items indicated with an asterisk (\*) are also exclusion criteria for patients

- i. Clinical evidence of significant cardiovascular, respiratory, renal, hepatic, gastrointestinal, hematological, neurological, psychiatric or other disease that may interfere with the objectives of the study and/or pose safety concerns.\*
- ii. Current symptomatic orthostatic hypotension or history of hypotensive response as defined by a reduction of  $\geq 30$  mmHg in systolic or  $\geq 20$  mmHg in diastolic BP.\*
- iii. Current symptoms of a functional gastrointestinal disorder assessed by questionnaire
- iv. Putative risk factors for pelvic floor trauma, i.e. six or more vaginal deliveries, birthweight >4500gms (macrosomia), or known 4th degree perineal tear
- v. Inability to withdraw medications prior to the baseline period and throughout the study (except as protocol defined rescue medications):
  - Medications that substantially alter GI transit \* including laxatives, magnesium and aluminum containing antacids, prokinetics, erythromycin, narcotics, anti-cholinergics, tricyclic antidepressants, SNRI and newer antidepressants
  - Selective serotonin reuptake inhibitor (SSRI) antidepressants are permissible at low, stable doses. All medications shall be reviewed and dis/approved by the principal investigator on a case by case basis. \*
  - Potent Cyp 3A4 inhibitors such as ketoconazole, itraconazole and ritonavir, nitrates and phosphodiesterase inhibitors \*

NOTE: stable doses of thyroid replacement, estrogen replacement, low dose aspirin for cardioprotection, and birth control (but with adequate backup contraception as drug-interactions with birth control have not been conducted) are permissible. \*
- vi. Stable dose of thyroxine will be permitted \*
- vii. Prolonged Q-Tc interval > 500 msec on ECG within the last three months\*
- viii. Estimated glomerular filtration rate (eGFR) < 60 mL/minute. \* Based on guidelines and recommendations from the National Kidney Disease Education Program (NKDEP) of the National Institutes of Health (NIH) and the Kidney Disease Outcomes Quality Initiative (KDOQI) of the National Kidney Foundation, the an eGFR using the Modification of Diet in Renal Disease (MDRD) Study

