
#### 4. Data and statistical analysis

a) Part A. Anal manometry will be analyzed by established techniques and summarized as anal resting and squeeze pressures, rectal and anal pressure and rectoanal gradient during evacuation. Rectal pressure-volume relationships will be summarized by the  $P_{r_{half}}$  during rectal compliance, rectal capacity, pressure and volume sensory thresholds for first sensation, desire to defecate, and urgency. During

sinusoidal oscillation, average rectal pressures and the variability in pressures over 20 min will be summarized.

The analysis will be based on analysis of covariance (ANCOVA) models to assess the pre-dug period for intervention effects with subject status and intervention type as the primary factors (a check for order effects of the intervention sequences will also be made, and the corresponding pre-stress response will be included as a covariate). Models with a subject status by intervention type interaction will also be examined. During period 2, subjects will have been randomized to drug or placebo (balanced on subject status) and use the same intervention sequence as the pre-drug period). The analysis of the post drug period will also be based on ANCOVA models incorporating subject status, intervention type, treatment group, and corresponding interactions (a check for order effects will again be made). The corresponding responses from the pre-stress interval from period 1 and VAS scores for stress and arousal will be used as covariates,

b) Part B.

- i. Endpoints. Symptoms and Signs of Chronic Constipation. The effects of alfuzosin compared to placebo will be assessed by evaluating
  - Bowel habits using a daily diary (Appendix 1) to record stool consistency (Bristol Stool Form scale), frequency, ease-of-passage and sensation of complete bowel emptying (yes/no)
  - Daily Abdominal Pain Scores (Appendix 2) collected as (a) most severe daily score and (b) overall average daily score).
  - Global Patient Treatment Assessments reporting outcomes on a weekly basis (Appendix 3) including overall relief and severity of constipation
  - Global Patient reported outcomes on a 2-week basis (Appendix 5)
  - Patient reported outcomes of other abdominal symptoms (Appendix 6)

Two outcomes will be derived from primary data.

  - Weekly rate of SBMs: a bowel movement (BM) is considered an SBM if no laxative, enema or suppository was taken in the preceding 24 hours.

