5. Sample size assessment. The sample size assessment is based on the variation in anal resting pressures in healthy subjects and patients with defecatory disorders and the effect of the  $\alpha_1$  receptor antagonist (indoramin) on anal resting pressure in a previous study. The CV (%) in anal resting pressure evaluated by the same technique in healthy women (<50 years old) and patients with defecatory disorders (<50 years old and resting pressures >90) was 20% (mean=93.7{SD=18.5}) and 11% (mean=102.9{SD=11.7}), respectively. In period 2 the sample size of 36 controls and 36 patients will yield 18 subjects per treatment arm (drug vs. placebo) in each subject group (control vs. patients). This should provide 80% power to detect a treatment effect size of roughly 15-20%, based on a two sample t-test with a two-sided alpha level of 0.05 separately in each subject group. The effect size is defined as the difference in group means as a percentage of the overall (both groups) mean value. The previous study suggested an effect size of 47% for drug effects. For part B, data pooled from constipation subjects imply differences between treatment groups of ~4 stools per week, differences in stool consistency scores of ~1.1 and differences in ease of passage scores of 0.8 could be detected with 80% power (2-sided alpha level of 0.05). It is anticipated that the ANCOVA models will provide similar power for somewhat smaller differences by incorporating the baseline values as covariates.
  6. Anticipated results and interpretation. We anticipate that: (i) alfuzosin will reduce anal resting pressure and increase the rectoanal gradient during simulated evacuation but not affect the squeeze increment; (ii) alfuzosin will attenuate the augmentation of anal pressure by mental stress; (iii) mental relaxation will reduce anal resting pressure to a greater extent after placebo than alfuzosin; and (iv) rectal compliance and the contractile response to sinusoidal oscillation will be lower in chronic constipation than in healthy subjects.

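### Patient-versus-control contrasts, above all Aim 4, are unrandomised and unmatched over ages 18 to 80, and no Part A model adjusts for age

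*Combined protocol and SAP*

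**What the plan says.** **Recruitment (B.1.a and B.1.b).** Controls are "Healthy women volunteers aged 18-80 years". The patient criteria cover the same range: "Inclusion Criteria for Patients (women aged 18-80 years". The protocol plans 36 women per group. It describes no matching and no balancing of the two groups on age.

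**Exclusions (B.1.c).** Only items marked with an asterisk also apply to patients. The obstetric item ("six or more vaginal deliveries, birthweight >4500gms (macrosomia), or known 4th degree perineal tear") has none, so it restricts controls only.

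**Part A models (B.4.a).** The pre-drug ANCOVA will "assess the pre-dug period for intervention effects with subject status and intervention type as the primary factors", and "the corresponding pre-stress response will be included as a covariate". For the post-drug models, which add treatment group and interactions, "The corresponding responses from the pre-stress interval from period 1 and VAS scores for stress and arousal will be used as covariates". No other covariates are named. For compliance and oscillation the section lists summary measures and names no model for comparing the groups.

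**Aim 4.** The hypotheses are that women with DD have higher rectal compliance and a weaker contractile response to oscillation than healthy women.

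**Planning data (B.5).** The variability of resting pressure was taken "in healthy women (<50 years old) and patients with defecatory disorders (<50 years old and resting pressures >90", although enrolment runs to 80.

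**The concern.** Drug versus placebo is randomised and balanced on subject status, but subject status itself is not randomised. Volunteers and clinic patients drawn from a 62-year age range may differ in age. If an anorectal measure also varies with age, an unadjusted contrast credits part of that age effect to DD.

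Aim 4 is where this matters most. It is purely a patient-control comparison, randomisation gives it no protection, and no baseline covariate is specified for it. A positive result could not be separated from an age difference, and a negative one could be an age difference hiding a real effect. The same question applies, more weakly, to the subject-status terms in the stress and relaxation models.

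The plan shows some awareness of age, since it restricted its planning data to women under 50, but nothing in the analysis section carries that through.

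**Working it through.** **1. The plan's own figure.** With 18 per arm and two-sided alpha 0.05, the two-sample t-test (noncentral t) has 80% power for these differences:
- controls (SD 18.5): 17.8, or 17.8/93.7 = 19.0% of the mean;
- patients (SD 11.7): 11.2, or 11.2/102.9 = 10.9%;
- pooled SD √[(18.5² + 11.7²)/2] = 15.5: 14.9, or 14.9/98.3 = 15.1%.

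The stated 15-20% is therefore reproduced as a rough range. It concerns the randomised drug comparison. The plan gives no such figure for patients versus controls.

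**2. The unadjusted patient-control test.** With 36 versus 36 there are 72 − 2 = 70 error degrees of freedom, the critical t is 1.994, and the difference detectable with 80% power is 0.67 within-group SD.

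**3. Bias from age.** Let ρ be the within-group correlation of age with the outcome and d the difference in mean age in SDs of age. If DD has no effect, the expected difference is ρ × d in outcome SDs. The noncentrality is ρd × √(36/2) = 4.243 × ρd. The documents give neither ρ nor d, so I assume ρ = 0.2 to 0.5 and d = 0.25 to 1.0. As a scale, ages spread evenly over 18 to 80 would have SD 62/√12 = 17.9 years, so d = 0.25 would be about 4.5 years and d = 1.0 about 18 years.

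**4. Detectable difference with age in the model.** This is approximately 0.669 × √[(1 − ρ²)(1 + d²/4)].

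| ρ | d | Bias (SD) | Noncentrality | False-positive rate, unadjusted | Detectable difference, adjusted (SD) |
|---|---|---|---|---|---|
| 0.2 | 0.25 | 0.05 | 0.21 | 5.5% | 0.661 |
| 0.5 | 0.25 | 0.125 | 0.53 | 8.2% | 0.584 |
| 0.3 | 0.5 | 0.15 | 0.64 | 9.6% | 0.658 |
| 0.2 | 1.0 | 0.20 | 0.85 | 13.3% | 0.733 |
| 0.4 | 0.75 | 0.30 | 1.27 | 24.1% | 0.655 |
| 0.5 | 1.0 | 0.50 | 2.12 | 55.3% | 0.648 |

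**5. Simulation check (4,000 runs per scenario).** For (ρ, d) = (0.3, 0.5), (0.4, 0.75) and (0.5, 1.0), the unadjusted test rejected a true null in 9.6%, 23.6% and 56.9% of runs. With age as a linear covariate the rates were 4.6%, 5.3% and 5.6%, and the mean bias was within 0.01 SD of zero. With a true difference of 0.67 SD, the adjusted test had 81-82% power. The simulation makes the age effect linear and equal in both groups, so it shows what adjustment achieves in that case, not that such an effect exists.

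**6. Cost.** One covariate takes the error degrees of freedom from 70 to 69 and the critical t from 1.994 to 1.995.

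**The case against.** The strongest reply is that the ANCOVA sentence concerns stress and relaxation effects, not Aim 4, and that those models are already partly protected. This is right. The pre-stress response absorbs at least part of any age-related difference in baseline pressure, leaving mainly age differences in the response to the interventions. The drug-versus-placebo effects are randomised and not confounded by age. For Aim 4, however, the reply exposes a larger gap: no between-group model is named. If one reads the opening statement about ANCOVA as covering compliance and oscillation too, the listed covariates still omit age.

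Two stronger readings are tempting, and the documents support neither.

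- *Age could account for the whole patient-control gap in resting pressure.* The planning means differ by 102.9 − 93.7 = 9.2, but those patients were selected for pressures above 90 and the healthy women were not, so the gap is partly made by selection. Resting pressure is not an Aim 4 outcome, and no age slope or age difference is given. One cited manometry study names age in its title, which shows neither the size nor the direction of an effect, and says nothing about compliance.
- *Adjusting for age and number of deliveries would remove the confounding with data already in hand.* Age is certainly available: eligibility and the eGFR formula both need it. Obstetric history is not a named item in the screening description or Table 1; for patients its recording can only be inferred from the general medical history. A delivery count would not capture birthweight or perineal tear, and cannot repair the lack of overlap that the control-only exclusion permits. Nor would adjustment correct the preference for patients with high resting pressure in initial studies (B.7).

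**Conclusion.** The point holds in a limited form. Patient-control comparisons are unrandomised and unmatched across 18 to 80 years, and no Part A model includes age. Exposure is greatest for Aim 4, smaller for the status terms in the stress and relaxation ANCOVAs, and absent for drug versus placebo.

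The size of the bias cannot be derived from the documents. Over the assumed ranges it runs from negligible (0.05 SD) to serious (0.50 SD, against a detectable difference of 0.67 SD). The upper end needs both a strong age correlation and a full-SD age imbalance. A middling case (ρ = 0.3, d = 0.5) roughly doubles the nominal 5% error, to 9.6%. The argument for acting is less that the bias is known to be large than that the protection costs almost nothing: under the same assumptions the adjusted detectable difference is 0.58 to 0.73 SD.

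**What to change.** - **Aim 4.** In B.4.a, state that each compliance and oscillation summary will be compared between groups with a linear model containing subject status and continuous age.
- **Other status effects.** Add continuous age as a covariate wherever a subject-status effect is estimated, keeping the pre-stress covariates already planned.
- **Reporting.** Give the age distribution by group and show the unadjusted estimate beside the adjusted one.
- **Obstetric history.** Where the medical history records it, report it by group and use it in a sensitivity analysis only, noting that the exclusion restricts controls alone.
- **Interpretation.** State that adjustment reduces confounding by measured factors, does not remove it, and does not correct the selection of patients for high resting pressure.

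This takes a few sentences in the analysis section and about one error degree of freedom out of about 70. Age needs no new data collection, and the sample size does not change.

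### Part A analyses controls and patients in one ANCOVA with no provision for unequal variances, although the drug effect is powered within each group and the planning SDs are 18.5 and 11.7

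*Combined protocol and SAP*

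**What the plan says.** Section B.4.a (Data and statistical analysis, Part A) puts both subject groups into the same models. For the period after dosing: "The analysis of the post drug period will also be based on ANCOVA models incorporating subject status, intervention type, treatment group, and corresponding interactions". The covariates are the pre-stress response from period 1 and the VAS scores for stress and arousal. The section does not mention a residual variance structure, a variance check or separate fits by group. It also does not say how a drug effect within controls or within patients will be obtained.

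Section B.5 (Sample size assessment) plans for 18 subjects per arm in each group and takes its power "based on a two sample t-test with a two-sided alpha level of 0.05 separately in each subject group". The CV of resting pressure in healthy women and in patients "was 20% (mean=93.7{SD=18.5}) and 11% (mean=102.9{SD=11.7}), respectively". The patient figures come from "patients with defecatory disorders (<50 years old and resting pressures >90"). The claim is: "This should provide 80% power to detect a treatment effect size of roughly 15-20" percent. Aim 1 states its hypothesis for healthy people and for patients with defecatory disorders.

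**The concern.** The powered question is the drug effect inside each group, but the model described is joint. With equal cells, an ordinary joint ANCOVA gives the two within-group drug contrasts essentially the same standard error, built from the average of the two residual variances. If controls vary more than patients, that standard error is too small for controls and too large for patients. A chance drug effect would be declared too often in controls, and power would be lost in patients, the group for whom a treatment is sought. The only variability figures in the plan differ by a factor of 1.58 in SD (2.50 in variance), so the question needs an answer before the data are analysed.

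**Working it through.** **Inputs.** From B.5: n = 18 per cell, SD 18.5 (mean 93.7) in controls, SD 11.7 (mean 102.9) in patients, two-sided alpha 0.05. From B.4.a: randomisation balanced on subject status. Assumed, because the documents do not give them: the correlation between baseline and post-drug pressure, and the residual SDs. One response per subject is used. The repeated interventions per subject are not modelled, and the plan does not state their covariance.

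**1. The plan's own figure.** Detectable difference at 80% power, two-sample t-test, 34 df, as a percentage of the planning mean:
- controls: 17.8 / 93.7 = 19.0%
- patients: 11.2 / 102.9 = 10.9%
- pooled SD: 14.9 / 98.3 = 15.1%

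The stated 15-20% is reproduced by the control SD (upper end) and the pooled SD (lower end). It is conservative for patients taken alone.

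**2. Standard errors, taking the raw SDs as residual SDs.** Pooled SD = √((18.5² + 11.7²)/2) = 15.48. SE = SD × √(2/18):
- pooled: 5.16
- controls' own: 6.17
- patients' own: 3.90

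**3. Type I error of the within-group tests.** Error = 2 × (1 − Φ(1.96 × 15.48 / group SD)):
- controls: 1.96 × 15.48 / 18.5 = 1.64, so 10.1%
- patients: 1.96 × 15.48 / 11.7 = 2.59, so 0.95%

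Simulation of the four-cell model (40,000 trials) gives 10.1% and 1.0%. Separate variances give 5.1% and 4.9%. Adding a baseline covariate with the same correlation in both groups (0 to 0.9) leaves about 10% and 1%. That is expected, because equal correlations keep the SD ratio at 1.58.

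**4. Sensitivity to the residual SDs.**

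| Assumption | Controls | Patients |
|---|---|---|
| Residual SD ratio 1.0 | 5.1% | 5.0% |
| Ratio 1.2 | 7.2% | 3.1% |
| Ratio 1.4 | 8.6% | 1.8% |
| Ratio 1.58 | 9.9% | 1.1% |
| Correlation 0.8 controls, 0.4 patients | 5.2% | 4.6% |
| Correlation 0.5 controls, 0.8 patients | 12.9% | 0.05% |
| SD gap due to baseline selection only | 5.0-5.5% | 4.7-5.4% |

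The last row follows from the restriction above 90. Cut a normal distribution with the control values at 90: a = (90 − 93.7)/18.5 = −0.20 and λ = φ(a)/(1 − Φ(a)) = 0.675. The SD becomes 18.5 × √(1 + aλ − λ²) = 11.8, against the 11.7 stated for patients. The mean becomes 93.7 + 18.5 × 0.675 = 106.2, against 102.9, so the match is not complete.

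**5. Power in patients with the planning SDs.** Without a covariate, the pooled test rejects beyond 1.995 × 5.16 = 10.3.
- 10% effect (10.3): Φ((10.3 − 10.3)/3.90) = 50% pooled, against 71% with own variance. At an assumed correlation of 0.5, simulation gives about 65-67% against 82-84%.
- 15% effect (15.4): Φ((15.4 − 10.3)/3.90) = 90% pooled, against 97%.
- 20% effect (20.6): above 99% pooled.

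**6. Joint-model tests.** The variance of the sum or difference of the two within-group contrasts is 6.17² + 3.90² = 53.3, and pooling gives 2 × 5.16² = 53.3. Simulated error is 5.3% for the drug main effect and 5.2% for drug by status.

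**The case against.** The strongest reply is that the plan never says it pools. It is silent on error structure, and the only within-group drug test it describes is the t-test run separately in each group, which uses that group's own variance and holds 5%. This stands as far as it goes: pooling is inferred from the ordinary meaning of ANCOVA. But the t-test appears only as the basis for power, and B.4.a names ANCOVA as the analysis. An analyst following that section literally would most naturally take within-group contrasts from the joint model with its single error term.

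The second reply is that 18.5 and 11.7 are raw SDs, whereas the model adjusts for the period 1 response. The patient SD also comes from women selected for pressure above 90. The eligibility criteria contain no such threshold, and section B.7 says only that patients with high resting pressure will be recruited for initial studies. Selection alone could produce nearly the whole gap, and then pooled error would be about 5% in both groups. This stands too, and the documents cannot separate that case from a true difference in residual SDs. The different CVs (20% and 11%) do not settle it, because the 11% comes from the same restricted sample.

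A reader might infer that the trial's tests will run at 10% and 1%, or that patients fall short of the promised power. The documents support neither: the first needs a residual SD ratio that they do not give, and the second fails at the planned effect size.

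**Conclusion.** The gap is real, but its size is conditional. The plan should say how within-group drug effects are obtained and with what variance. Error of about 10% in controls and 1% in patients follows only if the contrasts come from an ordinary joint ANCOVA and the residual SD ratio is near the planning ratio of 1.58. At a ratio of 1.2 it is about 7% and 3%, and under pure baseline selection about 5% in both. The power loss in patients matters for effects near 10%. At the planned 15-20% they keep about 90% or more even with pooling, using the planning SDs and no covariate. With balanced cells, the main effect and the interaction are not at issue. This is a cheap improvement that should be made, not a defect that undermines the trial. Not knowing the residual ratio is itself a reason not to build in the assumption that it equals 1.

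**What to change.** In the Part A models, allow the residual variance to differ by subject status, with Satterthwaite or Kenward-Roger degrees of freedom, or fit controls and patients separately. State that each within-group drug effect and its confidence interval use that group's own variance. This holds about 5% error whether or not the variances differ. The cost is a sentence in the analysis section and one model option, with no change to data collection or participants. If the variances are in fact equal, about 1-2 percentage points of power are lost (for example, 81% to 80%). The change should be made before unblinding.

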- a) Anorectal sensorimotor functions. After rectal cleansing with 1-2 sodium phosphate (Fleets®, C.B. Fleet, Lynchburg, VA) enemas, anorectal resting and squeeze pressures and rectal compliance and sensation will be evaluated before and after randomization to alfuzosin (2.5 mg oral) or placebo (Figure 1) in the Charlton 7 CRU. During each epoch (i.e., baseline or drug), pressures will be evaluated before and after patients are randomized to one of 6 sequences (orders) of 3 interventions (i.e., 2 stressors and active relaxation). The same stressor/relaxation sequence will be applied during pre-drug and post drug epochs. Anorectal assessments, which will be performed with standard techniques, include:
- Anal resting and squeeze pressures using high resolution manometry, similar to the procedure employed in the clinical lab and in recent studies;
  - Rectal compliance and sensation using a barostat/ polyethylene balloon. A conditioning distention from 0-40 mmHg in 4 mm steps at 15 second intervals will be performed. Ten minutes thereafter, the balloon will be distended from 0-44 mmHg or maximum tolerated pressure in 4 mmHg steps; sensory thresholds for first sensation, desire to defecate, and urgency will be recorded
  - Rectal ramp distention. Because the contractile response to distention is influenced by the rate of distention, a ramp distention to 200 mL over 1 minute will be performed; this will be sustained for 2 minutes. While (ii) is useful for characterizing quasi-static pressure-volume relationships representing colonic tone, ramp distentions can uncover the active contractile response to distention.
  - Rectal sinusoidal oscillation will be performed at 5 cpm for 20 minutes after distention to 125 mL. This paradigm is more sensitive than barostat-driven distentions for uncovering increased rectal stiffness in fecal incontinence but has not been evaluated in constipation

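### The post-drug model leaves out each woman's own pre-drug pressure response to the same task, a baseline already collected, and so gives up some precision in the tests of whether alfuzosin alters stress and relaxation effects

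*Combined protocol and SAP*

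**What the plan says.** Section B.3.a sets out two epochs on the study day, one before and one after alfuzosin or placebo. "During each epoch (i.e., baseline or drug), pressures will be evaluated before and after patients are randomized to one of 6 sequences" of two stressors and one relaxation task, and "The same stressor/relaxation sequence will be applied during pre-drug and post drug epochs". Each post-drug task value therefore has a pre-drug counterpart from the same woman, for the same task at the same place in the order.

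Section B.4.a gives the models. For the pre-drug period, "the corresponding pre-stress response will be included as a covariate", which shows that pre-stress means the reading before the task. The post-drug analysis uses "ANCOVA models incorporating subject status, intervention type, treatment group, and corresponding interactions (a check for order effects will again be made"). Its covariates are then listed: "The corresponding responses from the pre-stress interval from period 1 and VAS scores for stress and arousal will be used as covariates". The period-1 response to the task is not among them.

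Section B.6 names two results that depend on task response after drug: "alfuzosin will attenuate the augmentation of anal pressure by mental stress", and "mental relaxation will reduce anal resting pressure to a greater extent after placebo than alfuzosin". Section B.5 states that the sample size "will yield 18 subjects per treatment arm (drug vs. placebo) in each subject group (control vs. patients"). Its Part A power statement concerns the drug effect on resting pressure only.

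**The concern.** Women differ in resting anal pressure, and they may also differ in how much their pressure moves under stress or relaxation. A period-1 resting covariate deals with the first kind of difference. It does not directly address the second. Whatever part of a woman's reactivity is stable over the study day, and is not picked up by the VAS scores, stays in the residual of the post-drug model.

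This bears on Aims 2 and 3. They ask whether the task effect differs between alfuzosin and placebo, with 18 women per arm in each subject group and no power statement. The plan elsewhere accepts that a matching baseline helps. In Part B the corresponding baseline value is the primary covariate, and Section B.5 expects baseline adjustment to allow somewhat smaller differences to be detected. For a post-drug task response, the matching baseline is the pre-drug response to that task.

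**Working it through.** **1. The plan's own figure.** Inputs from Section B.5: 18 per arm, two-sided alpha 0.05, power 80%, resting pressure 93.7 (SD 18.5) in controls and 102.9 (SD 11.7) in patients. Detectable difference = SD × √(2/18) × (1.960 + 0.842) = 0.934 × SD.

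- Controls: 17.3, or 18.4% of the mean (17.8, or 19.0%, with the t distribution).
- Patients: 10.9, or 10.6% (11.2, or 10.9%, with t).
- Both groups together, SD about 15.5 and mean about 98.3: about 15%.

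The stated 15-20% reproduces for controls and for the pooled data, and is conservative for patients. It concerns resting pressure and is not in dispute.

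**2. Gain from one more baseline covariate.** Let r be the partial correlation of the post-drug task response with the pre-drug response to the same task, given the covariates already in the model. The residual variance is multiplied by 1 − r², and the equivalent sample size is 18/(1 − r²) per arm. The documents give no r, so the values are assumed.

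| r (assumed) | Variance cut | SE factor | Equivalent n per arm | Power of a contrast planned at 80% |
|---|---|---|---|---|
| 0 | 0% | 1.000 | 18 | 79.9% (one df lost) |
| 0.3 | 9% | 0.954 | 19.8 | about 84% |
| 0.5 | 25% | 0.866 | 24.0 | about 90% |

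**3. What r is plausible for the task-minus-rest contrast.** Take a favourable case: each woman's reactivity is identical in both epochs. Let V be the variance of resting pressure (18.5² = 342.25 in controls, 11.7² = 136.89 in patients). Assume ICC 0.8, so stable level is 0.8V and independent reading noise 0.2V, and a reactivity variance s² of 25 or 64 (SD 5 or 8 mmHg). VAS is left out because nothing is known of its correlation with pressure.

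- Variance of the period-2 change (task minus rest): s² + 0.4V. It is uncorrelated with period-1 rest.
- Variance of period-1 task pressure given period-1 rest: 0.36V + s².
- Covariance of the two: s².
- Proportional variance cut: s⁴ / [(s² + 0.4V)(0.36V + s²)].

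Controls: 625/(161.9 × 148.2) = 2.6% and 4096/(200.9 × 187.2) = 10.9%. Patients: 625/(79.8 × 74.3) = 10.5% and 4096/(118.8 × 113.3) = 30.4%. The plain correlation between the two epochs' changes, s²/(s² + 0.4V), is 0.15-0.32 in controls and 0.31-0.54 in patients.

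**4. The same inputs with a different outcome.** If the outcome is post-drug task pressure itself, adjusted for period-1 rest, the cut is [(0.16V + s²)/(0.36V + s²)]². Controls: (79.8/148.2)² = 29% and (118.8/187.2)² = 40%. Patients: (46.9/74.3)² = 40% and (85.9/113.3)² = 58%. With s² = 0 the formula still gives (0.16/0.36)² = 20%. That part comes from having a second reading of resting level and owes nothing to reactivity.

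**The case against.** The strongest reply is that this is a preference about precision and that the plan contains no error. That is right as far as it goes. A reader might infer that the drug comparison is biased or invalid without this covariate. The documents do not support that: drug is randomized, and omitting a pre-randomization covariate leaves the comparison valid.

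A second reply is that the benefit is easily overstated, and this also stands. A reader might take the 29-58% in step 4 as the gain for attenuation. Those figures belong to task pressure adjusted for period-1 rest, and they partly reflect a better estimate of level. A reader might also carry the table on to r = 0.7, which would give a 49% cut and 35 women per arm. The favourable inputs of step 3 imply correlations of at most 0.54, and nothing in the documents supports a higher value.

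Third, VAS stress and arousal scores are already covariates and may absorb some reactivity. That is why r has to be a partial correlation. VAS is a self-rating, however, and does not stand in for the pressure response.

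Fourth, the covariate sentence ends in a comma in this copy and Figure 1 is not shown, so text may be missing. Nothing elsewhere in the documents supplies the covariate.

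**Conclusion.** The point holds as a modest, nearly free gain in precision for the task-response comparisons of Aims 2 and 3. The text is clear that the period-1 covariate is the pre-task value, and the design supplies the matched task response before drug randomization.

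The size cannot be derived from the documents. On assumed partial correlations of 0 to 0.5, the variance falls by 0% to 25%. Under fully reproducible reactivity, ICC 0.8 and reactivity SD 5-8 mmHg, the task-minus-rest contrast gains roughly 3-11% in controls and 10-30% in patients. If individual reactivity is not reproducible between epochs, this contrast gains nothing. The change would not by itself give Aims 2 and 3 adequate power, and it does not affect the stated power for resting pressure.

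**What to change.** In Section B.4.a, add the period-1 pressure change for the same task (task minus pre-task value) as a covariate in the post-drug model for task response, beside the period-1 resting value. Specify it before unblinding. It is measured before randomization to drug, so it does not bias the drug contrast.

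The cost is one degree of freedom with a common slope across tasks, and no new data or procedures. If the covariate proves uninformative, a contrast planned at 80.0% power falls to 79.9%.
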